## **11.2      *Inspiratory Muscle Training Protocol:***

Based on the findings of a systematic review (Z. Sadek et al., 2018), it has been determined that to achieve significant improvements in inspiratory muscle strength, the threshold pressure for inspiratory muscle training (IMT) should be set at 60% of the maximal inspiratory mouth pressure (MIP). Consequently, the intervention protocol for IMT involves using a threshold-loaded IMT device (Threshold IMT Philips® Resironics, Inc). In the IMT group, the initial intensity of the inspiratory threshold will be set at 60% of each patient's initial maximal MIP, which is then readjusted after 2 weeks of training to maintain the 60% of MIP throughout the 4-week period. Rates of perceived inspiratory effort on a modified Borg scale will also be used to determine the highest tolerable load for each patient (at the 4-6 level of 10) (Borg, 1982; Wilson and Jones, 1989). Patients will perform IMT for 2 sets of 30 repetitions, with one-minute intervals between each set (McConnell, 2013; Z. Sadek et al., 2018). Throughout the training sessions, patients will be instructed to maintain diaphragmatic breathing. On the other hand, the Sham-control group will follow the same training program using the same device, but without any inspiratory load. Both groups will perform the training program twice a day, five days a week, for a total of 4 weeks, under the supervision of a physiotherapist (McConnell, 2013). The supervision will be conducted remotely through telerehabilitation, utilizing video calls to connect with the patients without requiring them to physically visit the healthcare facility. To familiarize the participants with the training procedure, both the IMT and Sham-control groups will undergo a session without any load on the day of the baseline assessments. Throughout the study, all participants will visit the healthcare facility for baseline assessments, final assessments, and an additional brief assessment session at the end of the second week of training to measure MIP and readjust the loading value. The assessment to be made at the end of the 2nd week of the 4-week training seasons will only include the assessment of inspiratory muscle function described in 11.1.5.

The Threshold IMT products will be obtained by researchers and provided to patients without any cost. A patient who loses the product before the study ends will be notified that he or she will be excluded from the study. The enrolled research subject is not responsible for returning the

PROTOCOL TITLE: Effects of high-intensity inspiratory muscle training as a pre-cardiac rehabilitation intervention on cardiovascular functions in patients with heart disease

Threshold IMT product upon completion of the research activities. There are no expected adverse events based on the product label.

## **12.0 Data and Specimen Banking\***

**12.1** The data will be banked for future use by sharing with all researchers for 5 years at least without any personal information of patients. All written data collection forms and digital data will be handled by principal investigator.. The principal investigator will be the person contacted and the authorizing authority in this regard.

**12.2 The data to be stored:** All written data collection forms, in addition to digital data that prepared for analysis.

**12.3 The procedures to release data:** Before using the data, those wishing to use it should contact the principal investigator via e-mail. In this e-mail, a state in general what the data will be used for and how it will be shared with whom. The principal investigator will be able to authorize the use of the data by providing a digitally signed pdf letter. Only academic researcher can obtain data.

## **13.0 Sharing of Results with Subjects\***

**13.1** Results (study results or individual subject results, such as results of investigational diagnostic tests, genetic tests, or incidental findings) will not be shared with subjects or others (e.g., the subject's primary care physicians). Only the involved researchers will be informed. Patients will not be informed about the change in MIP values.

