## 1.0 Study Summary

**Background / aim:** Endothelial function is closely associated with coronary artery health among individuals being treated for heart disease. An impairment in endothelial function promotes arterial stiffening that directly contributes to elevated systolic blood pressure as a result of increased vascular resistance. Inspiratory muscle training is simply a form of training consisting of repeated inspirations against a resistance. Inspiratory muscle training has also been applied to patients with chronic disease or as an additional therapy for cardiac rehabilitation and it has proven to be safe in these groups. Few studies in the literature examined the effects of high intensity inspiratory muscle training in this population, however, these studies did not examine the direct effects of inspiratory muscle training on vascular function. To the best of our knowledge, the effects of inspiratory muscle training in patients with heart disease on endothelial function and arterial stiffness prior to starting cardiac rehabilitation have not been investigated.

**Methods:** The study was designed as a randomized controlled trial. The demographic and clinical characteristics of the patients will be recorded after consent is obtained from the volunteer patients who meet the inclusion criteria. Subsequently, patients will be randomly divided into two groups (22 subjects in each group) for inspiratory muscle training (IMT) with 60% of maximum inspiratory pressure (MIP) or sham inspiratory muscle training (Sham-control), for 4 weeks. In both groups, before and after 4-week-training, resting blood pressure (systolic/diastolic), resting heart rate, endothelial function, arterial stiffness, functional exercise capacity, the severity of dyspnea and inspiratory muscle functions will be measured.

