#### **11.1.4 Evaluation of Functional Exercise Capacity (visit #1, 4-week visit)**

Submaximal functional exercise capacity will be evaluated with the 6-minute walking test (6MWT). 6MWT is a test that is frequently used in the evaluation of submaximal functional exercise capacity, has a low cost, provides important clinical results and is recommended by the guidelines

**PROTOCOL TITLE: Effects of high-intensity inspiratory muscle training as a pre-cardiac rehabilitation intervention on cardiovascular functions in patients with heart disease**

(ATS, 2002). As the standard protocol of the test, the person is asked to walk as fast as possible for six minutes in a continuous 30-meter corridor. Peripheral oxygen saturation, heart rate, perceived severity of dyspnea and leg fatigue (range 0-10) with the modified Borg scale are recorded before and after the test (ATS 2002; Borg, 1982). At the end of the test, the total distance walked is recorded in meters (Enright and Sherrill, 1998).

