**18.0 Provisions to Monitor the Data to Ensure the Safety of Subjects\***

The principal investigator will be primarily responsible for monitoring the safety of participants, and the safety and confidentiality of data. This will be done by following the best practices to ensure that we strictly adhere to the inclusion and exclusion criteria, and protections against risks outlines. The safety of each participant will be assessed on an individual basis throughout their involvement with the study. Any decline in function or participant responses that indicates a potential adverse effect will be reviewed individually and events will be reported to the IRB per UIC policy in a timely manner.

A member of the study personnel will be available to each participant throughout testing and will be monitoring participant safety. Participants will be instructed to immediately inform study personnel if any adverse effects of treatment are experienced. We will ask the participant to provide us with a phone number of a caregiver (or friend or family member) to contact in case of emergency. Any adverse events or unanticipated problems will be recorded and communicated to all study personnel as soon as possible. Study personnel will be trained to identify and manage adverse events or unanticipated problems involving risks to subjects or others. The PI will be notified immediately. Serious adverse events, study-related adverse events, and unanticipated problems will be reported within 24 hours to the UIC IRB. Participants will be removed from the study if the study procedures threaten the participants' safety or study procedures are unbearable. Any adverse events will be noted within the subject file.

In the event of injury related to this research, treatment will be available. However, the subject or his/her third party payer, if any, will be responsible for payment of this treatment. In the unlikely event that the subject requires emergency medical care during a study visit, 911 will be called

PROTOCOL TITLE: Effects of high-intensity inspiratory muscle training as a pre-cardiac rehabilitation intervention on cardiovascular functions in patients with heart disease

immediately. There is no compensation and/or payment for such medical treatment for such injury except as may be required by law.

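### Section 13.1 bars telling participants or their physicians about individual results and incidental findings, with no safety exception, and Section 18 neither supplies a route for non-emergency findings nor says that it overrides 13.1.

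*Protocol*

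**What the plan says.** **Disclosure (Protocol Section 13.1).** Study results and individual results are withheld. Incidental findings are named expressly: "incidental findings) will not be shared with subjects or others". Primary care physicians are the example given of those others. Only the researchers involved are to be informed, and a separate sentence keeps changes in MIP from patients. No exception is stated.

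**Safety (Protocol Section 18.0).** There is a general duty: "The safety of each participant will be assessed on an individual basis throughout their involvement with the study". A member of staff is present during testing and watches over the participant's safety. On deterioration, "Any decline in function or participant responses that indicates a potential adverse effect will be reviewed individually". On reporting, "Serious adverse events, study-related adverse events, and unanticipated problems will be reported within 24 hours to the UIC IRB". The principal investigator is told at once and study personnel are informed. On stopping, "Participants will be removed from the study if the study procedures threaten" their safety. An emergency at a visit leads to a 911 call.

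**What is measured.** Section 11.1.4 has staff note "Peripheral oxygen saturation, heart rate, perceived severity of dyspnea and leg fatigue", which "with the modified Borg scale are recorded before and after the test", at visit 1 and at week 4. Section 1.0 lists measurements "before and after 4-week-training, resting blood pressure (systolic/diastolic), resting heart rate", although Section 11.1 describes no blood pressure procedure.

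**Medical record (Protocol Section 11.0).** The study enters no results from its procedures in the medical record. The SAP does not address disclosure.

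**The concern.** Section 13.1 is a positive instruction, not silence. A staff member who follows it literally would withhold an incidental finding from the patient and from the patient's doctor, even one the investigator thought important but not an emergency.

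The population makes this matter. Under Section 7.1 participants have had CABG, percutaneous coronary intervention, heart failure and/or myocardial infarction, and they are seen before cardiac rehabilitation begins. Section 10.0 describes identification through clinician referral, so there will often be a clinician who could act. Because Section 11.0 keeps results out of the record, that clinician would not come across the finding there either. What is at stake is patient safety, not the validity of the comparison.

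**Working it through.** The plan gives no figure to reproduce and no formula applies. The check sets the two sections side by side and asks whether Section 18 covers a finding that 13.1 withholds.

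**Step 1: who is told under each provision.**

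| Provision | Trigger | Who is told or acts |
|---|---|---|
| 13.1 | Any individual result or incidental finding | Researchers involved only; subject and physician excluded |
| 18, staff presence during testing | Every test, baseline included | Study personnel |
| 18, individual safety assessment | Whole period of participation | No recipient stated |
| 18, review | Decline or response suggesting an adverse effect | Reviewed individually; events to the IRB |
| 18, event reporting | Adverse events, unanticipated problems | Study personnel and principal investigator; IRB within 24 hours for serious events, study-related events and unanticipated problems |
| 18, removal | Procedures threaten safety or are unbearable | Subject leaves the study; disclosure of the reason not addressed |
| 18, emergency | Emergency care needed at a visit | 911; the caregiver telephone number is also for emergencies |

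No row of Section 18 names the participant or the treating clinician as a recipient of a result that is important but not an emergency.

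**Step 2: a worked case.** At visit 1 the reading before the walk shows an abnormal resting saturation or heart rate. No earlier study value exists to decline from, and no loaded training has been given: the familiarisation session on that day is without load (Sections 5.1 and 11.2). The wording on decline and on adverse effects of treatment would therefore not ordinarily be triggered. The staff presence during testing and the individual safety duty do apply, so the reading should be noticed and the walk could be withheld. Once noticed, however, the only provision on passing the value to the patient or doctor is 13.1, and it says no.

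**Step 3: precedence.** Section 18 does not mention 13.1, and 13.1 does not mention Section 18. The general duty might be taken to prevail. Against that, 13.1 is the specific rule on disclosure and names incidental findings. The documents do not settle the question.

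**Step 4: exposure only.** Section 9.1 plans 44 participants, each scheduled for two walk tests: 44 × 2 = 88 scheduled pre-walk readings. With its 10% loss falling after baseline, 44 + 44 × 0.9 = 44 + 39.6, or about 84. The week-2 visit is not counted because it covers inspiratory muscle function only. These figures count occasions on which a finding could arise. They say nothing about how many would, and they depend on the assumed loss.

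**The case against.** The strongest reply is that Section 18 already protects these patients. Staff are present and watching at every test, baseline included; they are trained to manage adverse events; safety is assessed for each individual; and removal and 911 are available. This stands, and it limits the point. A reader might infer that the trial lacks safety monitoring, or that a baseline reading escapes Section 18 altogether. The documents support neither inference. What is missing is a disclosure route, not oversight.

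A second reply is that 13.1 reads like template text: it mentions genetic tests, which this protocol never performs, and it may never have been meant to limit Section 18. That is plausible, but template wording in an approved protocol still binds staff. For the same reason, a reader should not infer that investigators would in fact withhold an important finding. The documents show only what the rule says.

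Third, the consent pages were not available for this review, and the names of those who run cardiac rehabilitation are removed, so clinical follow-up may already exist. This is a genuine limit, but it does not change the rule in 13.1.

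Fourth, a reader might infer that the MIP sentence should also be loosened. Nothing in the documents supports this. None of the examples involves MIP, and in a sham-controlled trial a participant's MIP change could hint at allocation.

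Finally, telling a clinician might seem to clash with Section 11.0. It does not: that section restricts what the study enters in or takes from the medical record, not what is said to the participant or, with permission, to the clinician.

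**Conclusion.** The point holds as a gap in disclosure. Section 13.1 forbids passing individual results and incidental findings to the participant or physician without a safety exception. Section 18 provides no route for a clinically important non-emergency finding and claims no precedence.

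The change should be made because literal compliance is worse for the patient and the remedy is small. How often such a finding would arise cannot be computed from the documents, and the 84 to 88 readings are exposure, not risk. The conclusion rests on the protocol text alone and assumes that no other operative document, such as the consent form, already supplies the exception. Blood pressure is the weaker example, since only the Study Summary lists it; saturation and heart rate have a described procedure. There is no consequence for type I error, power, the sample size or the estimates.

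**What to change.** Add to Section 13.1:

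> *Exception: an incidental finding or safety measurement (for example heart rate, oxygen saturation or blood pressure) that the investigator judges clinically important for the participant's safety will be told to the participant and, with the participant's permission, to the treating clinician; Section 18 takes precedence over this section.*

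Leave the sentence withholding MIP change unaltered, and keep the Section 11.0 rule that the study enters no results in the medical record. If the consent form repeats the ban, bring it into line.

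The cost is one sentence, possible consent wording and an IRB amendment. The downside is occasional disclosure of a single safety value. Endpoints, sample size and analysis do not change.

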## **14.0 Withdrawal of Subjects\***

**14.1** Subjects will be withdrawn from the research without their consent according to the rules as follows; 1. Not attending more than 20% of supervised intervention sessions. 2. Not perform the measurements after the intervention (at the end of the 4th week). 3. Losing the product (Philips IMT) before the study ends. 4. Consent in writing that who wishes to end the study at any stage of the study.

**14.2** For patients meeting any of 14.1 (one of the above), the principal investigator will be notified. The principal investigator will notify that he/she has been terminated from the study by obtaining verbal consent from the relevant patient.

**14.3** Should the subject choose to withdraw, the health information already collected will continue to be used for research, however, no further health information will be collected. All health information and collected data will be stored coded on paper, electronically on UIC Health Data Box Folder. Only the PI and Co-Is will have access

PROTOCOL TITLE: Effects of high-intensity inspiratory muscle training as a pre-cardiac rehabilitation intervention on cardiovascular functions in patients with heart disease

to the key to the code that links coded data with the identity of the subject (which will be password protected).

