**5.2 Device Handling:** The Threshold IMT Philips products will be obtained by researchers and provided to patients without any cost. The Threshold IMT Philips products is a legally marketed device when used in accordance with its labeling. There are no expected adverse events based on the product label. They will be used only on subjects and be used only by authorized investigators. On the other hand, a patient who loses the product before the study ends will be notified that he or she will be excluded from the study.

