## **9.0 Number of Subjects**

**9.1** For the required sample size; on the basis of prior studies (Hermes et al., 2015; Dos Santos et al., 2019; Dos Santos et al., 2021), the sample size was calculated as 20 subjects per group ( $n = 40$  in total) for a significance level of 5%, a statistical power of 90%, and a difference in maximum inspiratory pressure (MIP) of at least 23 cmH2O between groups. However, to optimize the results, the required sample size was calculated as 44 participants,  $n=22$  participants per group, with consideration of a 10% loss at follow-up. Separately, after ethical approval, the ClinicalTrials.gov study registration will be done before the study starts.

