#### **11.1.3 Dyspnea Evaluation (visit #1, 4-week visit)**

The modified Medical Research Council (mMRC) dyspnea scale used in the evaluation of general dyspnea is a simple, valid and reliable five-item scale based on various physical activities that cause dyspnea. With this scale, patients are asked to mark the activity level that causes dyspnea (Bestall et al., 1999). There are many studies indicating that this scale is associated with dyspnea, arterial blood gases, health status, and lung function tests (Bausewein et al., 2007; Bestall et al., 1999; Wilson and Jones, 1989). The mMRC dyspnea scale attached end of this document.

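### Withdrawal for missed sessions or a lost device reads as ending follow-up, and with no analysis set named, these patients drop out of the randomized comparison by default

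*Protocol*

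**What the plan says.** Section 14.1 of the protocol lists four grounds for removal. Under rule 1 patients are "withdrawn from the research without their consent according to the rules as follows; 1. Not attending more than 20% of supervised intervention sessions". Rule 2 reads "Not perform the measurements after the intervention (at the end of the 4th week". Rule 3 is loss of the training device and rule 4 is the patient's own written wish to stop.

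Section 14.2 gives the consequence of meeting any rule: "The principal investigator will notify that he/she has been terminated from the study by obtaining verbal consent from the relevant patient". Section 5.2 says that "a patient who loses the product before the study ends will be notified that he or she will be excluded from the study", and section 11.2 repeats it.

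Section 14.3 covers data after withdrawal: "Should the subject choose to withdraw, the health information already collected will continue to be used for research". It adds that nothing further is collected, but it is worded for a patient who chooses to withdraw.

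Section 11.1 gives the visits. Dyspnea is typical: "Dyspnea Evaluation (visit #1, 4-week visit". The 6-minute walk, flow-mediated dilation and pulse wave velocity follow the same two visits. Inspiratory muscle function, which includes maximal inspiratory pressure (MIP), is also measured at week 2.

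Section 17.1 plans an ANCOVA with baseline as covariate. The SAP plans an analysis of variance on mean change. Neither names an analysis set or a method for missing data. Section 9.1 sizes the trial at 22 per group "with consideration of a 10% loss at follow-up".

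**The concern.** Rule 1 acts after randomization and depends on what patients do during treatment. The loaded arm trains at 60% of MIP and the sham arm trains without load, so attendance may relate to outcome differently in the two arms. If removed patients are not measured, the groups compared at week 4 are no longer the groups that were randomized. Two of the three primary endpoints (endothelial function and arterial stiffness) then have no post-baseline value for these patients. The week-2 MIP does not help, because no planned between-group model uses it.

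With no analysis set stated, a reader cannot tell who will be analysed, and in a trial of 44 that choice could be made after the data are seen.

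Two wording problems sit in the same section. The attendance rule can be read in two ways. And 14.1 removes patients without their consent, while 14.2 has the investigator obtain verbal consent to the termination.

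**Working it through.** **Sessions.** Section 11.2 gives 2 per day x 5 days x 4 weeks = 40 sessions, and 20% of 40 is 8. Rule 1 means either missing 9 or more of 40 or attending 8 or fewer. The first is the more natural reading.

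**Planned loss.** Section 9.1 reproduces as 20 x 1.10 = 22 per arm, 44 in total. Going from 22 to 20 is 2 lost per arm, or 4/44 = 9.1%. This is total loss. It includes patients who refuse or miss week 4 (rules 2 and 4), not only those removed under rules 1 and 3.

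**Bias model.** All of this is assumed, because the documents give no loss pattern or correlation. There are 22 per arm, no true effect, standard normal scores, and baseline to week-4 correlation r = 0.7. In each arm the patients lowest on a latent score are removed, and that score correlates ρ with the week-4 value.

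If a fraction q of an arm is removed, the mean week-4 value of those kept rises by about ρλ, with λ = φ(z_q)/(1 − q), and their baseline mean rises by rρλ. The shift left in the treatment estimate is therefore:
- ANCOVA: ρλ(1 − r²) = 0.51ρλ
- change-score ANOVA: ρλ(1 − r) = 0.30ρλ

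For 2 of 22 removed, λ = 0.180. For 4 of 22, λ = 0.323. With the tie in the loaded arm only:

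| Lost (loaded, sham) | ρ | ANCOVA by formula | ANCOVA simulated | Type I error |
|---|---|---|---|---|
| 2, 2 | 0.3 | 0.51 x 0.3 x 0.180 = 0.028 | +0.026 SD | 5.2% |
| 2, 2 | 0.5 | 0.51 x 0.5 x 0.180 = 0.046 | +0.043 SD | 5.5% |
| 2, 2 | 0.7 | 0.51 x 0.7 x 0.180 = 0.064 | +0.062 SD | 6.1% |
| 4, 1 | 0.5 | 0.51 x 0.5 x 0.323 = 0.082 | +0.080 SD | 6.5% |
| 4, 1 | 0.7 | 0.51 x 0.7 x 0.323 = 0.115 | +0.114 SD | 8.0% |

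The simulations used 400,000 trials per cell. Other cells, by ANCOVA unless stated:
- 4 versus 1 with ρ = 0.5 in both arms: +0.06 SD, 5.9%.
- 2 versus 2 with equal ties: 0.00 SD.
- 1 loaded versus 3 sham, tie of 0.5 in sham only: −0.06 SD, 6.0%.
- SAP change-score ANOVA, ρ = 0.5, loaded arm only: +0.03 SD, 5.1% (2, 2) and +0.05 SD, about 5.5% (4, 1).
- Loss acting only through baseline, 4 versus 1, ρ = 0.5: 0.00 SD with ANCOVA, −0.05 SD with the change score.
- r = 0.5 or 0.8 in place of 0.7, ρ = 0.5, loaded arm only: +0.064 or +0.031 SD (2, 2) and +0.116 or +0.057 SD (4, 1).

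**Power if everyone is analysed as assigned.** Section 9.1 gives no SD. A t test with 90% power at 20 per arm implies an effect of 1.052 SD, so an SD of 23/1.052 = 21.9 cmH2O. Suppose all 22 per arm are measured and loaded patients off training keep none of the effect. The mean difference falls to 1.052 x 20/22 = 0.956 SD with 2 of 22 off training, and to 1.052 x 18/22 = 0.861 SD with 4 of 22.

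| Analysis | 2 of 22 off training | 4 of 22 off training |
|---|---|---|
| Unadjusted t test | 86% | 77% |
| ANCOVA, r = 0.5 | 93% | 87% |
| ANCOVA, r = 0.7 | 99% | 96% |

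If half the effect is kept, the t test gives 90% and 87%. With only 20 per arm measured, 2 of them off training and no effect kept, it gives about 82%.

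**The case against.** The strongest reply is that little is at stake. At the planned loss the bias is a few hundredths of an SD even when loss is tied to outcome in one arm only, and no passage documents such a tie. Equal loss with equal ties gives none. Device loss has no evident link to arm or outcome. All of this stands. It limits the weight of the point but does not tell a reader who is analysed.

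A reader might infer that the protocol forbids measuring removed patients at week 4. It does not say so. The stop on data collection in 14.3 is confined to those who choose to withdraw, and for rules 1 and 3 the end of follow-up is inferred from the wording of 14.1, 14.2, 5.2 and 11.2. A reader might also infer that only good adherers are compared. That depends on the reading of rule 1. If it means attending 8 or fewer sessions, patients attending 9 to 31 stay in.

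Section 10 keeps study participation and cardiac rehabilitation apart because exercise improves cardiovascular function. Measuring a removed patient who has since begun rehabilitation brings that influence into the comparison. This is a fair objection, and the start date and a sensitivity analysis are needed to deal with it.

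Finally, analysing everyone as assigned dilutes the effect. It does, but a reader who infers that the trial must therefore be enlarged or accept lower power is relying on the unadjusted t test. The protocol's ANCOVA gives higher power at either assumed correlation.

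**Conclusion.** The point holds as a recommended change, not a fatal flaw. As written, the natural course is that patients removed for attendance or device loss have no week-4 value and leave the randomized comparison without anyone having stated or justified that choice.

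Under the assumed patterns the ANCOVA bias runs from zero to about 0.06 SD near the planned loss, and to about 0.11 SD if the loaded arm loses 4 and sham 1. The type I error is at most about 8%. These figures rest on assumed correlations and loss splits. The direction is unknown, and the documents do not support a claim that the result will favour the loaded arm. Because the 10% in section 9.1 is total loss, a remedy aimed at rules 1 and 3 removes only the part of the bias that those rules cause.

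**What to change.** **Protocol**
- In 14.1, 14.2, 5.2 and 11.2, state that missed sessions or device loss do not by themselves end follow-up. Invite every randomized patient who has not withdrawn consent, and for whom testing raises no safety concern, to the week-4 visit already scheduled.
- Leave the safety removals in section 18 unchanged. Whether such a patient continues training is for the sponsor to state.
- In section 10, say that a removed patient who has since started rehabilitation may still be measured, without delaying rehabilitation. Record the start date.
- Say which reading of the attendance rule is meant (missing 9 or more of 40, or attending 8 or fewer), and reconcile 14.1 with 14.2 on consent.

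**SAP**
- Primary analysis: all measured patients in the arm assigned.
- Secondary: a per-protocol analysis by attendance.
- Sensitivity: exclude patients measured after starting rehabilitation.
- Report missing week-4 data with reasons, by arm.

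**Cost.** This takes a protocol amendment with IRB review and possibly a consent change; the one revision on record marks both of its changes as consent changes. A few more patients travel at their own expense. The estimate becomes the effect of assignment, with the dilution shown above. Patients who refuse or miss week 4 remain missing.
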